## 2. SPECIFIC APPROACH BY AIM

AIM 1: The premise for this aim is that there is a need to develop widely-available, easilyimplementable method for accurate assessment of ECV in HD patients. The objective of this aim is to establish the association between ECV excess and IBPS from multiple treatments in hypertensive HD patients. We will test the working hypothesis that when measuring blood pressure every 30 minutes over 6 treatments, there will be a positive correlation between the mean systolic IBPS and the ECV/body weight measured with BIA in a cohort of 66 hypertensive HD patients. We have calculated the IBPS from a single treatment from 49 hypertensive HD patients in a more heterogeneous cohort who also have pre and post-HD BIA measurements. The median slope was -3.36 mmHg/hour (interquartile range -9 mmHg/hr, +3.5 mmHg/hour). There is a positive correlation between the IBPS and the ratio of ECV/body weight measured after HD (Pearson correlation coefficient 0.4, p=0.008). The post-HD correlation was 0.5 in men (n=32. p=0.01), but was 0.3 in the smaller group of women (n=17, p=0.2). It is necessary to demonstrate that the overall relationship between IBPS and ECV/body weight 1) persists when evaluating IBPS from multiple recent HD treatments and 2) is stronger in a more homogeneous cohort of HD patients without the extremely high or low intradialytic blood pressures that are more likely related to comorbid medical diseases than changes in ECV. It is also necessary to better define the association of this relationship with gender in a larger number of subjects with more equal distribution of men and women.

**RESEARCH DESIGN AIM 1:** We will use a cross sectional study design to determine the association between systolic IBPS and measurements of post-HD ECV/body weight using BIA in hypertensive HD patients. Limitations of BIA include that it cannot be used in patients with amputations or implanted metal prostheses due to inaccurate measurements. It cannot be used in pregnant individuals or those with cardiac defibrillators or pacemakers due to safety concerns. For this reason, additional exclusion criteria unique to this aim will be patients with 1) amputations of major extremity, 2) cardiac defibrillator or pacemaker, or 3) implanted metallic device (see Exclusion Criteria #10-12 above).

# Study Procedures:

- 1. Intradialytic Blood Pressure Slope: We will obtain recorded blood pressure measurements from the prior 6 treatments. We will calculate the average systolic IBPS (mmHg/hour) using linear regression analysis. The slope will be our primary independent variable.
- 2. Extracellular Volume Excess: We will use whole body multifrequency BIA (Impedimed SFB7) to measure ECV, intracellular volume, and total body volume before and 20 minutes after a mid-week HD treatment. We will use the ratio of post-HD ECV/body weight (L/kg) as our primary dependent variable. This is a recognized metric for determination of ECV excess[9].

### Statistical Analysis Plan and Power Calculation for Sample Size (Aim 1)

This aim's primary outcome is the correlation between mean IBPS and post-HD ECV/body weight. We will determine this with Pearson correlation analysis. In our preliminary data analysis of 49 HD patients, we demonstrated a significant association between ECV/body weight and systolic IBPS from one HD treatment (r=0.4, p=0.008). We aim to establish that an even stronger correlation exists in a more homogeneous population with less extremes of blood pressure and blood pressure changes (see Exclusion criteria 3-8 above). We also aim to establish associations within each gender. Assuming 80% power at a 0.05 significance level, we would need the following sample sizes to show the following correlations: 15 subjects for r=0.6, 23 subjects for r=0.5, 33 subjects for r=0.4 using Pearson correlation analysis. To confirm our assumption of normal distribution, we would need at least 30 subjects. We intend to recruit at least 66 subjects (33 of each gender) to ensure that we can demonstrate a strong correlation within each gender. Our expected Aim 2 sample size is 74 subjects (most of which will have BIA measurements), so we expect to have more than adequate sample size for Aim 1. Exploratory analyses will include correlation of ECV/body weight with diastolic blood pressure slope and overall change in blood pressure from pre to post dialysis as well as correlations involving ECV/total body volume with IBPS.

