### **EXPECTED OUTCOMES (Aim 1)**

We expect, for our primary outcome, that there will be a positive correlation between post-HD ECV/body weight and the mean IBPS of 0.6. We expect that the standard deviation in our cohort's IBPS will be smaller than that of our preliminary data cohort due to 1) a more homogenous population (see Exclusion criteria 3-8) excluding patients whose blood pressure changes are more likely to be related to ECV-independent comorbidities (autonomic neuropathy, medication non-adherence, advanced heart failure) and 2) calculation of the mean IBPS over 6 treatments, not a single treatment. We expect the ECV/body weight to be higher in men than women, but the correlations between ECV/body weight and IBPS will be similar. We expect that the association between IBPS and *pre*-HD ECV/body weight will not be as strong as with the slopes and *post*-HD ECV/body weight because pre-HD measurements are more reflective of acute, not chronic ECV excess. Based on our preliminary data, we do not expect as strong a correlation will exist with ECV/total body volume and IBPS.

[figure not shown]

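### The Aim 1 primary correlation pools men and women without adjustment, although the plan expects ECV/body weight to differ by sex; if IBPS does not differ by sex, the pooled r understates the within-sex r

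*Combined protocol and SAP*

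**What the plan says.** The Aim 1 statistical section defines the endpoint: "This aim's primary outcome is the correlation between mean IBPS and post-HD ECV/body weight". The method follows: "We will determine this with Pearson correlation analysis". No covariate, partial correlation or rule for combining sex-specific coefficients is given. The working hypothesis, in the opening of Aim 1, concerns "ECV/body weight measured with BIA in a cohort of 66 hypertensive HD patients", so the natural reading is a single coefficient over men and women together.

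The Expected Outcomes section for Aim 1 gives one anticipated value, that "there will be a positive correlation between post-HD ECV/body weight and the mean IBPS of 0.6". It then adds: "We expect the ECV/body weight to be higher in men than women, but the correlations between ECV/body weight and IBPS will be similar".

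Analyses by sex are planned as well: "We also aim to establish associations within each gender". They set the recruitment target: "We intend to recruit at least 66 subjects (33 of each gender) to ensure that we can demonstrate a strong correlation within each gender".

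**The concern.** The plan's own expectation is a common association within each sex plus a shift in the level of ECV/body weight between the sexes. A correlation adjusted for sex estimates that common association. A raw pooled correlation in general does not, because the between-sex spread in ECV/body weight enlarges the denominator while adding nothing to the numerator unless IBPS also differs by sex.

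This matters because the size of the coefficient is the result of Aim 1. The aim is to validate IBPS as a metric of volume and to show a stronger correlation than the preliminary 0.4. A coefficient that depends on how far apart men and women lie, and on the sex mix (32 men and 17 women in the preliminary data, 33 and 33 planned), is hard to interpret against either goal.

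**Working it through.** **The plan's own figures.** The Aim 1 statistical section gives 15, 23 and 33 subjects for r = 0.6, 0.5 and 0.4 ("Assuming 80% power at a 0.05 significance level", sidedness not stated). With an exact test of zero correlation:

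| r | Stated n | One-sided n | Two-sided n |
|---|---|---|---|
| 0.6 | 15 | 15 | 19 |
| 0.5 | 23 | 23 | 29 |
| 0.4 | 33 | 37 | 46 |

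The first two reproduce only as one-sided, and the 33 reproduces under neither. This is a separate matter, but it bears on how far the within-sex analyses can be relied on at r = 0.4.

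**Inputs.** From the documents: expected r = 0.6; preliminary r = 0.4; n = 66, split 33 and 33; alpha 0.05, taken here as two-sided. Assumed, because the documents give no value: d, the sex difference in ECV/body weight, and e, the sex difference in IBPS (men minus women), both in within-sex SDs.

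**Pooled coefficient, equal groups.** Within-sex covariance is r_w and between-sex covariance is d·e/4. The total variances are 1 + d²/4 and 1 + e²/4. Hence

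r_pooled = (r_w + d·e/4) / √[(1 + d²/4)(1 + e²/4)].

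**Power.** By Fisher z, power = Φ(atanh(r)·√(n − 3) − 1.96), with n − 4 in place of n − 3 for the sex-adjusted correlation. Exact calculations agree to within one percentage point.

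**Case 1: IBPS does not differ by sex (e = 0).** The formula reduces to r_w / √(1 + d²/4).

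| d | Divisor | r_w = 0.6 becomes | Power, n = 66 | r_w = 0.4 becomes | Power, n = 66 |
|---|---|---|---|---|---|
| 0.5 | 1.031 | 0.58 | >99.9% | 0.39 | 90% |
| 1.0 | 1.118 | 0.54 | 99.7% | 0.36 | 84% |
| 1.5 | 1.250 | 0.48 | 98.6% | 0.32 | 75% |
| Sex-adjusted | – | 0.60 | >99.9% | 0.40 | 92% |

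**Case 2: IBPS also differs by sex (not stated in the documents).** With d = 1 and r_w = 0.6, the denominator is 1.118 × 1.031 = 1.152.
- e = −0.5: (0.6 − 0.125)/1.152 = 0.41, power about 94%.
- e = +0.5: (0.6 + 0.125)/1.152 = 0.63.
- With no within-sex association and e = +0.5: 0.125/1.152 = 0.11, rejected in about 14% of studies against a nominal 5%.

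**Preliminary data.** Combining 0.5 in 32 men and 0.3 in 17 women on the Fisher scale: (29 × 0.549 + 14 × 0.310)/43 = 0.471, so r = 0.44, against 0.4 overall. That fits mild dilution, but the gap is within rounding and sampling error.

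**Within-sex analyses at n = 33.** Exact two-sided power is 65% for r = 0.4, 86% for 0.5 and 97% for 0.6.

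**Testing whether the sexes differ.** For 0.5 against 0.3, the difference in Fisher z is 0.549 − 0.310 = 0.240, with standard error √(1/30 + 1/30) = 0.258. The ratio is 0.93, giving about 15% power.

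**The case against.** Four arguments favour leaving the plan alone.

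1. **Within-sex correlations are already planned and set the sample size.** They are free of the sex shift, so an association absent in both sexes would be expected to show as absent there. This stands, and it is why they should not be demoted. But they are not named as the primary outcome, no rule links them to it, and at r = 0.4 their power is only 65%.

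2. **At the expected 0.6 the test is safe.** This also stands: dilution alone leaves power above 98%. What remains is an understated estimate in an aim whose result is that estimate.

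3. **A raw correlation may be the right target.** Table 2 of Aim 2 applies the same slope cut-offs to both sexes, and the 0.4 benchmark is itself a raw coefficient. If the whole sex difference in ECV/body weight were volume excess, the raw value would suit that use. The documents do not say that it is. The argument justifies reporting the raw value alongside, but it does not remove the mismatch with the plan's expectation of similar within-sex correlations.

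4. **Nothing shows confounding.** A reader might infer that the pooled coefficient is confounded by sex, or that it could produce an association that exists in neither sex. That needs IBPS to differ by sex, and no section reports such a difference. A null association within both sexes also sits poorly with the preliminary 0.5 in men and 0.3 in women. The stronger reading is not supported.

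**Conclusion.** The concern holds in a limited form. The named primary analysis does not match the association that the plan expects. With a sex shift in ECV/body weight and none in IBPS, it understates that association by about 3% at 0.5 SD, 11% at 1 SD and 20% at 1.5 SD (one minus the reciprocal of the divisor). At the expected within-sex r of 0.6 this affects the estimate and hardly touches power. At 0.4 it costs between about 2 and 17 percentage points of power against the adjusted analysis.

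These sizes rest on assumed sex differences, equal numbers of men and women, equal within-sex SDs and a two-sided test. Confounding remains a conditional possibility that adjustment would also cover, and should not be reported as a defect that the documents demonstrate. The change is worth making because it is nearly free, not because Aim 1 is likely to fail without it.

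**What to change.** In the Aim 1 statistical section, name as primary the Pearson partial correlation of mean six-treatment IBPS with post-HD ECV/body weight, adjusted for sex. A Fisher-z combination of the two within-sex coefficients would serve equally well. In addition:

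- Report the raw pooled r beside it, for comparison with the preliminary 0.4.
- Keep the correlations in men and in women as planned analyses, each with a confidence interval.
- Treat any IBPS-by-sex term as exploratory. With about 15% power to separate 0.5 from 0.3, a non-significant result would not show that the sexes are alike.

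The cost is one sentence and one degree of freedom. Sex is already needed for the bioimpedance calculation and is the randomisation stratum. The planned 66 subjects suffice, since the adjusted analysis has 92% power at r = 0.4.

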8.	Intradialytic Clonidine Use	This can acutely influence intradialytic blood pressure in an ECV-independent way. This is used to treat severe hypertension during dialysis, and these patients frequently have ECV-independent etiology of hypertension, including possible medication non-adherence	
9.	Documented Antihypertensive Medication Non-adherence	This can acutely influence intradialytic blood pressure in an ECV-independent way.	
Aim 1 C			
10.	Amputated Extremity (excluding fingers, toes, hands, or feet)	Bioimpedance measurements of extracellular water are less accurate if all 4 major limbs are not present.	
11.	Presence of cardiac defibrillator, pacemaker	The current from the bioimpedance electrodes may interfere with the function of these devices	
12.	Presence of metal prostheses	Bioimpedance measurements are less accurate if implanted metal is present	

Eligible subjects agreeing to participate in all aims will be assigned to one of two study groups based on computer-generated randomization stratified by gender: IBPS-based management or Standard of Care (detailed in Aim 2). The presence of contraindications to BIA (see Table 1, #10-12) would not exclude a subject from participating in Aims 2 and 3. Such subjects would complete all study procedures except the BIA and NICOM. The outcomes of Aims 2 and 3 (ambulatory blood pressure and intradialytic hypotension) would still be ascertained. Eligible subjects not willing to undergo randomization into a 16 week trial (Aims 2-3) may participate in the BIA and measurements in Aim 1 only.

In short subjects may participate in Aim 1 only, Aims 2 and 3 only, or all Aims based on individual exclusion criteria and preference. We have successfully recruited more than 125 HD patients over the past several years for various prospective research studies and continue to maintain support from DaVita dialysis units (see Letters of Support).

Study Procedures: All procedures will be conducted by authorized personnel from the UT Southwestern research team consisting of the principal investigator and research nurses/coordinators.

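### Aim 1: 33 subjects do not give 80% power for r=0.4 (65% two-sided, 76% one-sided), and the sample sizes for r=0.5 and r=0.6 hold only for an undeclared one-sided test

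*Combined protocol and SAP*

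**What the plan says.** The Aim 1 section on statistical analysis and power takes the correlation between mean intradialytic blood pressure slope (IBPS) and post-dialysis ECV/body weight as its primary outcome, tested by Pearson correlation. The premise is "Assuming 80% power at a 0.05 significance level", and the sizes given are "15 subjects for r=0.6, 23 subjects for r=0.5, 33 subjects for r=0.4 using Pearson correlation analysis". Sidedness is not stated there or elsewhere for Aim 1, although the working hypothesis is worded as a positive correlation.

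The last figure then sets the target: "We intend to recruit at least 66 subjects (33 of each gender) to ensure that we can demonstrate a strong correlation within each gender". The section adds that Aim 2 should bring in 74 subjects, most of them with bioimpedance, "so we expect to have more than adequate sample size for Aim 1".

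Two other places give the relevant effect sizes. Expected Outcomes (Aim 1) predicts that "there will be a positive correlation between post-HD ECV/body weight and the mean IBPS of 0.6", with similar correlations in men and women. Section 2 (Aim 1) reports preliminary single-treatment data from 49 patients: "Pearson correlation coefficient 0.4, p=0.008" overall, 0.5 in 32 men (p=0.01), while the correlation "was 0.3 in the smaller group of women (n=17, p=0.2").

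**The concern.** The three sample sizes do not follow from one calculation. Two of them match a one-sided test; the third matches neither a one-sided nor a two-sided test at the stated power. The third is also the one carried forward as the number per gender.

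The within-gender analysis is a stated purpose of Aim 1, prompted by the weaker preliminary correlation in women. If the true correlation in women lies nearer the preliminary values than 0.6, a non-significant result in 33 women is likely enough to matter: 35% at r=0.4 and 60% at r=0.3, two-sided. Beside a significant result in men, that could be read as a sex difference when it reflects low power.

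**Working it through.** **Inputs.** Power 80%, alpha 0.05, Pearson test of zero correlation, and the pairs (r, n) = (0.6, 15), (0.5, 23), (0.4, 33), all from the Aim 1 power section. Sidedness is not given, so both readings are shown.

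**Method.** Exact power for bivariate-normal data: the test statistic is t = r√(n−2)/√(1−r²) on n−2 degrees of freedom. Given the sampled slopes, it follows a noncentral t with noncentrality ρ√V/√(1−ρ²). Power is averaged over V, a chi-square on n−1 degrees of freedom. A simulation of 200,000 trials at n=33, r=0.4 gave 65.2% two-sided and 76.2% one-sided, in agreement with the exact values below.

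**The plan's figures.**

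| r | Stated n | Power, one-sided | Power, two-sided | n for 80%, one-sided | n for 80%, two-sided |
|---|---|---|---|---|---|
| 0.6 | 15 | 80.6% | 70.1% | 15 | 19 |
| 0.5 | 23 | 81.0% | 71.0% | 23 | 29 |
| 0.4 | 33 | 76.4% | 65.4% | 37 | 46 |

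One-sided, 15 and 23 reproduce exactly and 33 does not. Two-sided, none reproduces.

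**Hand check with Fisher's z.** n = ((z_α + z_power)/atanh r)² + 3, with z_power = 0.842 and atanh 0.4 = 0.4236.

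- One-sided: ((1.645 + 0.842)/0.4236)² + 3 = 37.4, so 38.
- Two-sided: ((1.960 + 0.842)/0.4236)² + 3 = 46.7, so 47.

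The approximation runs one subject above the exact result and leads to the same conclusion.

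**What 33 per gender and 66 pooled can detect (exact).**

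| True r | n=33, two-sided | n=33, one-sided | n=66, two-sided | n=66, one-sided |
|---|---|---|---|---|
| 0.3 | 40% | 53% | 70% | 80% |
| 0.4 | 65% | 76% | 92% | 96% |
| 0.5 | 86% | 92% | 99% | >99% |
| 0.6 | 97% | 99% | >99% | >99% |

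With n=33, 80% power is reached at r = 0.465 two-sided or 0.418 one-sided (Fisher's z: 0.471 and 0.425). The two-sided chance that both genders are significant, with the same r and 33 in each, is 0.654² = 43% at r=0.4 and 0.971² = 94% at r=0.6.

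**Which sidedness the preliminary p-values imply.**

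- n=49, p=0.008: for any r that rounds to 0.4 (0.35 to 0.45), the one-sided p is at most 0.0068, so 0.008 is out of reach. The two-sided p runs from 0.0012 to 0.0137 and equals 0.008 near r=0.375.
- n=32, p=0.01: for r from 0.45 to 0.55, the one-sided p is at most 0.0049 and the two-sided p at most 0.0098. Two-sided fits, but only near the lower rounding edge of r.
- n=17, p=0.2: r=0.3 gives 0.24 two-sided and 0.12 one-sided. With rounding this does not discriminate.

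**The case against.** The strongest reply is that nothing in the design depends on r=0.4. The plan expects 0.6 overall and similar values in each gender, because slopes are averaged over six treatments in a narrower population. At 0.6 the power with 33 per gender is 97% two-sided, and the primary analysis is pooled. On that view, one of three scenario figures is wrong and no design number has to move. This stands as a limit on the consequences. It does not make the figure right, and the plan offers 33 per gender as an assurance when the only observed value in women is 0.3.

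A second reply is that the hypothesis is directional, so the one-sided reading is natural and the gap is only 33 against 37. That is fair on size, but a directional hypothesis is not a declared one-sided test. A one-sided calculation treating the slopes as fixed comes closer still, with 79.0% at n=33 and 34 needed. However, it gives 13 and 21 for the other two correlations, so it does not explain the list, and it does not suit two measured variables.

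Third, how preliminary p-values were reported does not settle how the planned test will be run, and the check in men is marginal. Both points are accepted. The n=49 check is clear, but it only suggests that two-sided testing was used so far. Finally, the plan names no formal test of a sex difference, so the misreading described above is a risk and not a planned step.

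**Conclusion.** The concern holds. At 80% power and a 0.05 level, 33 subjects are too few for r=0.4 by 4 (one-sided) or 13 (two-sided). The other two figures are correct only for a one-sided test that the plan does not declare. Since 15 and 23 match the exact one-sided method, which gives 37 for r=0.4, 33 may be a slip for 37; this is an inference that the document does not confirm.

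The consequence is confined to the within-gender aim when the true correlation is below about 0.47 two-sided or 0.42 one-sided. The pooled primary outcome is adequately powered. These results assume bivariate-normal data and a null correlation of zero. The correction should be made, but it does not threaten the trial.

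**What to change.** - Declare the Aim 1 test as one- or two-sided.
- Replace the list with 19, 29 and 46 (two-sided, in line with the preliminary p-values) or 15, 23 and 37 (one-sided).
- State that 33 per gender has 80% power only for correlations of about 0.47 or more (0.42 one-sided), and confine the claim of ample sample size to the pooled analysis.
- As secondary improvements, report each gender's correlation with a confidence interval, and rest any statement about a sex difference on the interval for the difference. Say also how 33 women with bioimpedance will be reached: 33 of the 74 Aim 2 subjects is 45%, and the documents give no sex mix for the units. If women are assumed to be 30% to 50% of recruits, 74 yields about 22 to 37 before bioimpedance exclusions. The existing route by which subjects "may participate in the BIA and measurements in Aim 1 only" can fill a gap.

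The cost is wording only, with no added subjects or procedures. The one drawback is that the stated within-gender power looks less favourable.

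### Aim 1 asks how the IBPS–ECV relationship depends on gender but plans only separate correlations in men and women, with no estimate of the difference

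*Combined protocol and SAP*

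**What the plan says.** The Aim 1 rationale (section 2, Specific Approach by Aim) reports preliminary results by gender: "The post-HD correlation was 0.5 in men (n=32. p=0.01), but was 0.3 in the smaller group of women (n=17, p=0.2". It then says: "It is also necessary to better define the association of this relationship with gender in a larger number of subjects", and asks for a more even mix of men and women.

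The Aim 1 statistical section takes the correlation of mean IBPS with post-HD ECV/body weight as the primary outcome: "We will determine this with Pearson correlation analysis". On gender it says: "We also aim to establish associations within each gender". The recruitment target follows: "We intend to recruit at least 66 subjects (33 of each gender) to ensure that we can demonstrate a strong correlation within each gender". The exploratory analyses listed are the diastolic slope, the pre-to-post change in blood pressure, and ECV/total body volume.

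Expected Outcomes (Aim 1) predicts a primary correlation of 0.6. It expects higher ECV/body weight in men, "but the correlations between ECV/body weight and IBPS will be similar".

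No section of the document adds a comparison of the two correlations, an IBPS-by-gender interaction, or a confidence interval for the difference.

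**The concern.** The rationale and the expected outcomes pose a between-gender question, and the analysis plan answers a within-gender one. A significant correlation in one gender and a non-significant one in the other is not evidence that the correlations differ. Significance in both is not evidence that they are similar.

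The preliminary data already show this ambiguity: p=0.01 in men and p=0.2 in women, from correlations that are not distinguishable from each other. The planned analysis could return the same pattern in new patients and leave the reader to compare two p-values. At stake is the interpretation of Aim 1 by gender, which could be an apparent men-only association produced by chance or a claim of similarity that nothing supports.

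**Working it through.** **Inputs.** From the Aim 1 statistical section: 33 per gender; 80% power; alpha 0.05, sidedness not stated; required n of 15, 23 and 33 for r=0.6, 0.5 and 0.4. From Expected Outcomes: r=0.6. From the Aim 1 rationale: r=0.5 (n=32) in men and r=0.3 (n=17) in women.

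**1. The plan's own sample sizes.** The n giving 80% power for the Pearson test under bivariate normality (by simulation):

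| r | Stated n | One-sided n | Two-sided n |
|---|---|---|---|
| 0.6 | 15 | 15 | 19 |
| 0.5 | 23 | 23 | 29 |
| 0.4 | 33 | 37 | 46 |

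The first two stated figures match a one-sided test. The 33 for r=0.4 matches neither. Because sidedness is not stated, both are carried below, with two-sided as the main case.

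**2. Chance that exactly one gender is significant when the true r is the same in both.** The two genders are independent samples, so with power P in each the chance is 2P(1−P). At n=33:

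| True r | P, two-sided | 2P(1−P) | P, one-sided | 2P(1−P) |
|---|---|---|---|---|
| 0.4 | 0.654 | 45% | 0.764 | 36% |
| 0.5 | 0.863 | 24% | 0.922 | 14% |
| 0.6 | 0.971 | 6% | 0.986 | 3% |

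Example: 2 × 0.654 × 0.346 = 0.453. Taking the plan's 80% power at face value gives 2 × 0.8 × 0.2 = 32%.

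**3. Uneven split (assumption).** The plan targets 33 of each gender. If 66 subjects instead split as in the preliminary cohort, there would be 66 × 32/49 ≈ 43 men and 23 women. The chance is then Pm(1−Pw) + Pw(1−Pm), two-sided:
- r=0.4: 0.775 × 0.511 + 0.489 × 0.225 = 51%
- r=0.5: 0.941 × 0.290 + 0.710 × 0.059 = 32%
- r=0.6: 0.993 × 0.112 + 0.888 × 0.007 = 12%

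**4. The preliminary contrast.** Fisher z difference: (0.549 − 0.310)/√(1/29 + 1/14) = 0.74, p=0.46. The correlations are given to one decimal. With 0.45 to 0.55 in men and 0.25 to 0.35 in women, p runs from 0.26 to 0.71. No value in that range indicates a difference.

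**5. What an estimate of the difference would deliver with 33 + 33.**
- Standard error: √(1/30 + 1/30) = 0.258
- 95% CI half-width: 1.96 × 0.258 = 0.51 on the Fisher z scale
- If one gender's estimate were 0.6 (z=0.693), estimates in the other from tanh(0.693 − 0.506) = 0.18 to tanh(0.693 + 0.506) = 0.83 would give an interval that includes no difference.
- Power for 0.5 against 0.3: the difference is 0.240, and 0.240/0.258 = 0.93 standard errors, so power is about 15% (two-sided 0.05).

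**The case against.** The strongest reply is that the statistical section sets itself only the task of showing an association within each gender, and within-gender Pearson tests do that. The plan nowhere says that discordant p-values will be read as a sex difference, or that two significant results will be read as similarity. The rationale itself refers to the smaller number of women and answers with a larger, more balanced sample. The prediction of similar correlations is an expectation, not a planned test. All of this is fair, and a reader who infers that the plan commits to a wrong inference goes beyond the text. What stands is that the rationale and the expected outcomes raise a between-gender question that no analysis addresses.

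Two further readings are tempting and not supported. One is that a one-gender-only result is likely without qualification. At r=0.6, which the plan expects, the chance is only 3% to 6%. It is large only if the true correlation is nearer 0.4, although that is the value behind 33 per gender and the overall preliminary correlation. The other is that the gender result decides whether one ultrafiltration algorithm is justified for both sexes. The documents do not say so. Table 2 is a single algorithm whose cutoffs come from quartiles of the 49-patient preliminary cohort, and the Aim 2 section on potential problems keeps Aim 2 worthwhile even if the Aim 1 hypothesis fails.

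It is also true that a difference test would have little power here. That is a reason to report an interval, not a reason to leave the comparison to two p-values.

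**Conclusion.** The concern holds in this limited form: Aim 1 poses a between-gender question and plans no analysis that can answer it. With equal true correlations and 33 per gender, chance alone gives significance in exactly one gender about 45%, 24% or 6% of the time two-sided at r=0.4, 0.5 or 0.6 (36%, 14% or 3% one-sided). These figures assume bivariate normality and exactly 33 in each gender; the uneven-split figures rest on a further assumption that departs from the plan's target.

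The gap does not depend on r. At r=0.6 both genders would usually be significant, yet that would not demonstrate the similarity the plan predicts. The question is secondary within Aim 1. It leaves the overall primary correlation and the randomized comparison untouched.

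**What to change.** In the Aim 1 statistical section:

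- Name the difference between the male and female correlations (Fisher z), with its 95% CI, as the analysis that answers the gender question. Correlation is the right scale because the plan's prediction is about correlations.
- Add, as supportive, the IBPS-by-gender interaction from one linear model of post-HD ECV/body weight on IBPS, gender and their product. This compares regression slopes, which can disagree with the correlations if the spread of either variable differs by gender, so the text should say that the Fisher z difference governs.
- Report each within-gender r with its 95% CI.
- State that separate p-values will not be used to claim either a difference or similarity.

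The cost is a few lines of SAP text and one extra model, with no added subjects or measurements. The downside should be written down as well: with 33 + 33 the interval has a half-width of about 0.51 in Fisher z and power for a difference is low, so the result is an estimate. A non-significant difference will not establish that the correlations are close.
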